HIV	Human Immunodeficiency Virus
ICF	Informed Consent Form
ICH	International Conference on Harmonisation
IRB	Institutional Review Board
MOP	Manual of Procedures
N	Number (typically refers to participants)
NIH	National Institutes of Health
OHRP	Office for Human Research Protections
OHSR	Office of Human Subjects Research
PHS	Public Health Service
PI	Principal Investigator
PMW	Post-Mavyret weeks
POW	Post-operative weeks
QA	Quality Assurance
QC	Quality Control
SAE	Serious Adverse Event/Serious Adverse Experience
SOP	Standard Operating Procedure
SVR	Sustained virologic response
UNOS	United Network for Organ Sharing
US	United States

CONFIDENTIAL

This material is the property of the NYU School of Medicine and Langone Medical Center. Do not disclose or use except as authorized in writing by the study sponsor
Interventional Template Version: 28 APR 2017

Protocol Summary

[figure not shown]
Title	A single-center pilot study of the use of hepatitis C positive donors for hepatitis C negative heart transplant recipients with post-transplant treatment of hepatitis C viremia with Mavyret
Short Title	HCV positive heart donors
Brief Summary	Patients who are hepatitis C negative and are on the waiting list for a heart transplant will be enrolled. Study subjects will receive a heart transplant from a deceased donor who has tested positive for hepatitis C. Recipients will undergo surveillance for the development of hepatitis C viremia post-transplant. Those who develop viremia will be treated with an FDA-approved drug, Mavyret, which is a pan-genotypic hepatitis C treatment with a cure rate of over 98%. Treated patients will be monitored in order to ensure that cure of hepatitis C viremia with sustained virologic response has been achieved.
Phase	Pilot study
Objectives	To determine safety and efficacy of the strategy of transplantation of hearts from HCV positive donors (with or without evidence of active HCV viremia). To characterize the incidence of HCV viremia in recipients whose heart donors were HCV positive. For recipients who develop viremia, to characterize the time course of the development of viremia, and subsequent clearance of viremia after treatment with Mavyret.
Methodology	Open label, single treatment arm
Endpoint	Percentage of patients with sustained virologic response after treatment for HCV after heart transplant. Incidence of viremia after receiving a heart transplant from a donor who tests positive for hepatitis C.
Study Duration	Two years
Participant Duration	One year
Duration of IP administration	Eight weeks
Population	Adult patients active on the UNOS waiting list for a heart transplant
Study Sites	Single center (NYU Langone Hospital)
Number of participants	Ten patients
Description of Study Agent/Procedure	The heart transplantation will be performed per standard of care techniques, and all post-transplant management of the transplanted organ, including immunosuppression, will be carried out per standard of care. The study-specific interventions will be surveillance for the development of hepatitis C viremia post-transplant, the treatment of viremia with an FDA-approved drug, and then surveillance for sustained virologic response post-treatment.
Reference Therapy	Not applicable
Key Procedures	Monitoring for transmission of hepatitis C after heart transplant, treatment of viremia if it develops, and monitoring for response to treatment.
Statistical Analysis	In this small pilot study, descriptive statistics will be used.

CONFIDENTIAL

This material is the property of the NYU School of Medicine and Langone Medical Center. Do not disclose or use except as authorized in writing by the study sponsor

Interventional Template Version: 05 JAN 2017

Schematic of Study Design

CONFIDENTIAL

This material is the property of the NYU School of Medicine and Langone Medical Center. Do not disclose or use except as authorized in writing by the study sponsor
Interventional Template Version: 28 APR 2017

1 Key Roles

Principal Investigator

[name]
Associate Professor of Medicine
Clinical Director, Heart Failure Program
Medical Director, Heart Transplant and Ventricular Assist Device Program
The Leon H. Charney Division of Cardiology, NYU Langone Health
[name]
[REDACTED]
[REDACTED]

Co-Investigators:

[name]
Professor of Surgery
Surgical Director, Heart Transplantation and Mechanical Circulatory Support
NYU Langone Cardiothoracic Surgery Associates
[name]
[name]
[REDACTED]
[REDACTED]

[name] PhD
Assistant Professor of Surgery
Vice Chair for Research, NYU Langone Transplant Institute
[name],
[name]
[REDACTED]
[REDACTED]

[name]
Professor of Medicine
Director, Hepatology
NYU Langone Hepatology Associates
[name]
[name]
[REDACTED]
[REDACTED]

[name]
Associate Director of VAD and Heart Transplant
NYU Langone Cardiothoracic Surgery Associates
[name]

2.1 Background Information and Relevant Literature

In New York state, 2840 patients have received heart transplants since the year 2000. In that time, however 835 patients either died on the waiting list or became too sick for transplant [1]. Thus, for every 4 patients waitlisted in New York, one patient will die or become too sick for transplant before an organ becomes available. The shortage of organs available for heart transplantation directly results in loss of life.

At the same time, since 2000, in New York alone, 3,081 donor hearts were discarded because of donor history of HCV infection or exposure [2]. With the availability of new and well-tolerated direct-acting antiviral agents, cure rates for chronic HCV infection approach 100% [3]. Treatment of HCV naïve transplant recipients who develop donor-derived HCV infection post-transplant would be expected to be equally successful. Thus, if post-transplant antiviral treatment could enable HCV positive heart donors to be utilized for negative recipients, then the current donor pool has the potential to eliminate waitlist mortality.

CONFIDENTIAL

This material is the property of the NYU School of Medicine and Langone Medical Center. Do not disclose or use except as authorized in writing by the study sponsor
Interventional Template Version: 28 APR 2017

There is, in fact, precedent for this as a viable strategy to narrow the gap between organ supply and demand. A recently study in which HCV positive donor kidneys were transplanted into HCV negative recipients demonstrated both excellent outcomes in terms of allograft function, and 100% HCV cure rates among the recipients [4]. Other ongoing and unpublished series of kidney transplant recipients [5] and of heart transplant recipients [6] have observed that only about 70% of HCV negative recipients who receive an organ from a HCV positive donor actually develop HCV viremia post-transplant. This is not surprising since the designation for HCV donor positivity by UNOS is a positive test for *either* anti-HCV antibody or HCV RNA. Donors who test positive for HCV antibody alone may have a falsely positive test, or may have had a prior exposure to HCV with subsequent virus clearance; in either scenario, there would be no risk of transmission of HCV infection to a recipient. It is estimated that 33% of donors designated as HCV positive are, in fact, non-viremic [7].

In this pilot study we propose utilizing HCV positive donors for HCV negative patients on the waiting list for a heart transplant at NYU Langone. We will propose careful early post-transplant surveillance for the development of HCV viremia. We anticipate that approximately one-third of the patients will not develop viremia, despite the donor designation HCV positive. We anticipate that two-thirds of patients will develop early post-transplant HCV viremia. These patients will be immediately treated with an FDA-approved anti-HCV therapy which we expect will cure the HCV.

Willingness to participate in this trial will afford patients quicker access to heart transplantation, and will have the potential to reduce waitlist mortality.

2.2 Name and Description of the Investigational Agent

Mavyret (glecaprevir/pibrentasvir)

Manufacturer: AbbVie, Inc., North Chicago IL

Mavyret is an FDA-approved, marketed drug clinically indicated for the treatment of HCV infection in patients without cirrhosis.

Its formulation is as an oral tablet containing two antiviral agents: glecaprevir and pibrentasvir. Glecaprevir is an inhibitor of the HCV NS3/4A protease which is essential for viral replication. Pibrentasvir is an inhibitor of the HCV NS5 protease which is necessary for RNA replication and virion assembly. Mavyret is active against all known strains of HCV.

2.2.1 Preclinical Data

In vitro studies demonstrating efficacy of glecaprevir and pibrentasvir at preventing replication of all strains of HCV were published prior to the initiation of clinical trials for these agents. In vitro the two agents act synergistically and have high potency with low rates of resistance. [8]

2.2.2 Clinical Data to Date

In Phase 3 clinical trials, 8 weeks of Mavyret therapy achieved high rates (98%) of SVR across all genotypes (1-6) of HCV in patients with HCV infection without cirrhosis. Clinical trials involved over 2300 patients in 27 countries. Based on the results of clinical trials, the FDA approved Mavyret for use in the treatment of HCV (all strains) in patients without cirrhosis. (ClinicalTrials.gov identifiers:

NCT02651194, NCT02642432, NCT02640482, NCT02636595, NCT02604017, NCT02446717, NCT02640157, NCT02243293) [9-14].

Included in the clinical trial populations were patients with severe renal impairment (stage 4 or 5 CKD). In this population Mavyret was found to be effective in achieving a high rate of SVR and no dosing adjustment was required [15].

CONFIDENTIAL

This material is the property of the NYU School of Medicine and Langone Medical Center. Do not disclose or use except as authorized in writing by the study sponsor
Interventional Template Version: 28 APR 2017

2.2.3 Dose Rationale (if applicable)

The dose used will be the standard dosing regimen for its FDA approved indication, three tablets taken once daily with food (total daily dose: glecaprevir 300mg and pibrentasvir 120mg)

2.3 Rationale

There is a vast shortage of available organs for lifesaving heart transplants. Donors with history of HCV represent an unutilized source of organs that could potentially eliminate the current waiting list mortality. With the emergence of new, FDA approved treatments, HCV disease is now curable in nearly 100% of patients who contract it. By transplanting patients with HCV positive donor hearts, this study will offer the benefit of avoiding waiting list mortality, followed by treatment (with the expectation of cure) of HCV in the event of transmission.

2.4 Potential Risks & Benefits

2.4.1 Known Potential Risks

Risks of treatment failure: HCV mutation can lead to drug resistance and treatment failure. In patients administered Mavyret, the risk of this was 2% or less. For patients with treatment resistant HCV, rescue therapy with alternative agents can result in cure of up to 100% depending upon the genotype. Guidelines for the treatment of resistant HCV strains are published and updated regularly [16].

Risks of treatment intolerance: Over multiple clinical trials, the overall rate of medication related adverse events leading to permanent discontinuation prior to completion of an 8-week course of Mavyret therapy was 0.1% [17].

Risk of acute hepatitis C infection: Acute hepatitis C is asymptomatic in 66-75% of patients. The risks of acute HCV leading to fulminant hepatic failure are believed to be very low, however case reports of this do exist [18]. During the time that patients are acutely infected with hepatitis C infection, it is possible that patients could transmit infection to other individuals, if others individuals are exposed to the patient's blood. Family members who, for instance, assist patients with medical care such as diabetic blood sugar monitoring, could potentially be exposed to hepatitis C if they were to sustain a needlestick injury from a needle used by the patient. The risk of an infected individual transmitting hepatitis C via a needlestick exposure is approximately 5%. Patients in the study will be counseled to use caution to prevent blood exposure to other individuals and will be asked to notify the study team immediately if they believe any individuals were exposed to their blood during the duration of the study participation.

Risk of chronic hepatitis C infection: Patients who prove refractory to all therapy including rescue therapy and develop persistent viremia are at risk to develop chronic HCV infection which has the potential to cause cirrhosis/end-stage liver disease, the potential for the need for liver transplantation and/or death. We expect our treatment failure rate in this study to be 0%, therefore we expect the risk of chronic HCV infection to be 0%. In the event of a treatment failure, the risks of developing chronic HCV must be considered. It is estimated that approximately 15-30% of patients with chronic HCV develop cirrhosis/end-stage liver disease over 20-30 years [19]. This risk should be compared to the risk of death on the heart transplant waiting list. The reported one-year mortality for a waitlisted patient without a transplant is as high 26.7% [20].

The efficacy of HCV treatment with Mavyret is high (98%). The efficacy of rescue therapies approaches 100%. Even in the event of a treatment failure, the risk of cirrhosis and liver disease secondary to chronic HCV are low. We believe that the survival benefit of receiving an earlier heart transplant, by accepting an organ from a HCV positive donor, far outweighs the risks of HCV exposure and possible treatment failure.

CONFIDENTIAL

This material is the property of the NYU School of Medicine and Langone Medical Center. Do not disclose or use except as authorized in writing by the study sponsor
Interventional Template Version: 28 APR 2017

2.4.2 Known Potential Benefits

The benefit of this study is the ability to obtain a lifesaving heart transplant rather than risk death while waiting on the list for a HCV negative organ.

3 Objectives and Purpose

3.1 Primary Objective

This pilot feasibility study is being conducted to determine safety and efficacy of the strategy of transplantation of hearts from HCV positive donors (with or without evidence of active HCV viremia) into HCV negative recipients on the NYU Langone Health heart transplant waiting list, with subsequent anti-HCV therapy to treat infection in the recipient.

3.2 Secondary Objectives

Secondary objectives will include characterization of the incidence of HCV viremia in recipients whose heart donors were HCV positive.

For those who develop viremia we will also characterize the time course of the development of viremia, and subsequent clearance of viremia after treatment.

4 Study Design and Endpoints

4.1 Description of Study Design

This will be an open-label, single arm, single center trial of the use of HCV positive heart donors for HCV negative recipients, followed by treatment of HCV infection in recipients who develop viremia.

4.2 Study Endpoints

4.2.1 Primary Study Endpoints

The primary endpoint will be percentage of patients with sustained virologic response after treatment for HCV after heart transplant.

This endpoint was chosen as primary because it will enable us to evaluate the safety of transient exposure to HCV at the time of heart transplantation. The expectation is that all patients who develop HCV viremia will achieve SVR (cure) following treatment with Mavyret.

4.2.2 Secondary Study Endpoints

Secondary endpoints will include:

1-year patient survival rates in HCV negative heart recipients who receive a heart transplant from a HCV positive donor.

Incidence of acute HCV viremia among HCV negative recipients who receive a heart transplant from a HCV positive donor.

These endpoints will enable us to assess the risks associated with this approach to heart transplantation and will allow us to better understand the risks of this approach to risks associated with remaining on the waiting list for a HCV-negative organ offer.

5 Study Enrollment and Withdrawal

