5.4 Strategies for Recruitment and Retention

Recruitment of patients will occur during routine evaluation visits to determine candidacy for a heart transplant at NYU Langone Health. Patients will be informed of the option to enroll in this study, and if interested, detailed information pertaining to the risks and benefits of the trial will be provided.

The signing of the acknowledgment to consider participation in the study will occur in the outpatient clinic. No additional information about potential candidates will be collected to determine interest or candidacy for this trial than would otherwise be normally collected as per standard of care for evaluation for a heart transplant.

Written informed consent for actual enrollment in the study will occur in the inpatient setting once a viable organ offer has been identified and the patient is admitted for potential transplantation.

The target sample size will be 20 patients.

CONFIDENTIAL

This material is the property of the NYU School of Medicine and Langone Medical Center. Do not disclose or use except as authorized in writing by the study sponsor
Interventional Template Version: 28 APR 2017

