5.6 Total Number of Participants and Sites

20 patients are expected to be enrolled and transplanted. No sites outside of NYULMC will enroll patients.

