7.3.4 Final Study Visit - for all patients

CONFIDENTIAL

This material is the property of the NYU School of Medicine and Langone Medical Center. Do not disclose or use except as authorized in writing by the study sponsor
Interventional Template Version: 28 APR 2017

POW52 (+/- 14 days): FINAL ASSESSMENT AT 12-months post-transplant

- In person visit, record vital signs
- Record standard of care labs: hematology, biochemistry, coagulation, HBV serologies and NAT, HIV serologies
- Collect study labs: HCV NAT and serology

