10.5 Sample Size

10 patients are expected to enroll in this trial.

We expect that less approximately 70% of patients will develop evidence of HCV infection transmitted from the HCV-positive donor and will be treated for HCV infection. We expect that 100% of the patients who are treated for HCV infection will achieve SVR.

This is a single-arm study with no comparison group. The power to detect a difference in observed versus expected depends upon the true efficacy of the therapy. The reported efficacy of the therapy is 98%. With an estimated 7 patients who will be treated, a single treatment failure will be regarded as a significant deviation from the expected outcome.

11 Source Documents and Access to Source Data/Documents

Source data is all information, original records of clinical findings, observations, or other activities in a clinical trial necessary for the reconstruction and evaluation of the trial. Source data are contained in source documents. Examples of these original documents, and data records include: hospital records, clinical and office charts, laboratory notes, memoranda, subjects' diaries or evaluation checklists, pharmacy dispensing records, recorded data from automated instruments, copies or transcriptions certified after verification as being accurate and complete, microfiches, photographic negatives, microfilm or magnetic media, x-rays, subject files, and records kept at the pharmacy, at the laboratories, and at medico-technical departments involved in the clinical trial. It is acceptable to use CRFs as source documents. If this is the case, it should be stated in this section what data will be collected on CRFs and what data will be collected from other sources.

The study case report form (CRF) is the primary data collection instrument for the study. All data requested on the CRF must be recorded. All missing data must be explained. If a space on the CRF is left blank because the procedure was not done or the question was not asked, write "N/D". If the item is not applicable to the individual case, write "N/A". All entries should be printed legibly in black ink. If any entry error has been made, to correct such an error, draw a single straight line through the incorrect entry and enter the correct data above it. All such changes must be initialed and dated. DO NOT ERASE OR WHITE OUT ERRORS. For clarification of illegible or uncertain entries, print the clarification above the item, then initial and date it.

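### One-year survival in transplanted recipients, with no comparator, cannot inform the risk of this approach against staying on the waiting list, as Protocol 4.2.2 says it will

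*Protocol*

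**What the plan says.** Protocol 4.2.2 lists two secondary endpoints. One is "1-year patient survival rates in HCV negative heart recipients who receive a heart transplant from a HCV positive donor"; the other is the incidence of acute HCV viremia in the same recipients. It then says that these endpoints will help the team "better understand the risks of this approach to risks associated with remaining on the waiting list".

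The survival endpoint is set up as follows:

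- **Clock.** Protocol 7.3.4 sets the last visit at "POW52 (+/- 14 days): FINAL ASSESSMENT AT 12-months post-transplant".
- **Entry.** Protocol 5.4 states: "Written informed consent for actual enrollment in the study will occur in the inpatient setting once a viable organ offer has been identified". Section 7.3.2 places this at Day -1 to 0.
- **Analysis.** Protocol 10.4.3 and SAP 1.4.3 say that survival will be readily apparent from routine follow-up and UNOS reporting. They name no interval, benchmark or test. Protocol 10.4 limits the analysis to descriptive statistics, and 10.4.6 and 10.5 say there is no comparison group.

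The waitlist figure is in Protocol 2.4.1: "The reported one-year mortality for a waitlisted patient without a transplant is as high 26.7" percent.

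The number of patients is stated two ways. Protocol 10.5 says "10 patients are expected to enroll in this trial", and the Protocol Summary agrees. Protocol 5.6 says "20 patients are expected to be enrolled and transplanted", and 5.4 also gives 20.

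**The concern.** To weigh accepting an HCV-positive heart against waiting, one needs outcomes under both choices, from a common starting point, in comparable patients. The trial observes one side only. Every patient in the survival denominator has already received an organ, and the trial collects nothing on patients who keep waiting.

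The rationale in 2.3 and 2.4 rests on avoiding death on the waiting list. Once 4.2.2 has promised to inform that question, a reader of the results may set the observed post-transplant mortality beside 26.7% and take the gap as the benefit of the strategy. The trial cannot supply that inference.

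**Working it through.** **1. Is there a figure of the plan's own to reproduce?** For survival, no: no precision, power or margin is stated. The only derivable figure in 10.5 concerns treatment, 10 × 0.70 = 7 treated patients, and it is arithmetically right.

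**2. The two quantities side by side.**

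| | Trial endpoint | Waitlist figure |
|---|---|---|
| Population | Recipients of an HCV-positive heart | Waitlisted patients without a transplant |
| Time origin | Transplant | Not stated |
| Size or interval | N of 10 or 20; no interval planned | None given; described as an upper figure |
| Comparator in the trial | None | Not applicable |

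The mismatch in population and the missing comparator do not depend on N. Protocol 2.1 also gives waitlist counts for New York since 2000 (835 patients who died or became too sick, against 2840 transplanted), but these are not one-year mortality.

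**3. Precision of the survival endpoint.** With 0 deaths among n patients, the exact (Clopper-Pearson) upper limits for mortality are:

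- two-sided 95%: 1 − 0.025^(1/n)
- one-sided 95%: 1 − 0.05^(1/n)

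For n = 10, the two-sided limit is 1 − 0.025^(1/10) = 30.8%, so survival could be as low as 69.2%. The one-sided limit is 1 − 0.05^(1/10) = 25.9%. For n = 20, the two-sided limit is 1 − 0.025^(1/20) = 16.8%.

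| Deaths / n | Two-sided exact 95% upper limit | Includes 26.7%? |
|---|---|---|
| 0/10 | 30.8% | Yes |
| 1/10 | 44.5% | Yes |
| 0/20 | 16.8% | No |
| 1/20 | 24.9% | No |
| 2/20 | 31.7% | Yes |

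**4. How far the 0/10 result depends on method.** The two-sided 95% Wilson limit is 27.8%, which includes 26.7%. The Jeffreys limit is 21.7%, which does not. If true mortality were 26.7%, the chance of no deaths in 10 would be 0.733^10 = 4.48%. That is also the one-sided p-value. The two-sided exact p-value is 0.072 (minimum likelihood) or 0.090 (doubled). The smallest n at which zero deaths brings the two-sided exact limit below 26.7% is 12 (26.5%); at n = 11 it is 28.5%.

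**The case against.** The strongest reply is that the plan makes no such comparison. Section 4.2.2 speaks only of better understanding, the sentence covers viremia incidence as well as survival, and the analysis sections name neither a waitlist benchmark nor a test. No decision or halting rule depends on the sentence. This stands, and it limits the point to an overclaim. It does not rescue the sentence, which still assigns the endpoints a purpose the design cannot serve.

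Four stronger readings are tempting, and the documents do not support them.

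- **That the plan sets trial survival against 26.7%.** The figure appears in 2.4.1, in a discussion of chronic HCV. There, "This risk should be compared to the risk of death on the heart transplant waiting list" refers to cirrhosis and end-stage liver disease after treatment failure. No section pairs 26.7% with the survival endpoint.
- **That survivor bias necessarily favours the strategy.** Patients who sign the acknowledgement at screening and die before an offer never enter the cohort, which matters if the question is whether to opt in. But if the question is whether to accept a given offer, time zero is the offer, which is close to transplant. Recipients are credited with no waiting time, and early post-operative deaths count. Since the origin of the 26.7% is not stated, neither the direction nor the size of a bias can be established.
- **That even a perfect result cannot exclude 26.7%.** This holds at N = 10 with a two-sided exact or Wilson interval. It fails with a one-sided exact or Jeffreys limit, and it fails at N = 20 with 0 or 1 deaths.
- **That concurrent recipients of HCV-negative hearts would close the gap.** They share the transplant time origin, but they inform the effect of donor type, not the risk of waiting.

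**Conclusion.** The point holds as an overclaim of limited weight. A single-arm cohort of transplanted patients, followed from transplant, cannot show how this approach compares with remaining on the waiting list, whichever N applies. This conclusion needs no assumption about the 26.7% figure.

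The precision finding is secondary and conditional. It takes 26.7% at face value, although 2.4.1 presents it as an upper figure with no sample size or interval, and it assumes complete one-year follow-up so that survival is a simple proportion. On those terms the best possible result at N = 10 leaves mortality up to 30.8% compatible with the data (two-sided exact 95%), and at N = 20 up to 16.8%. A narrower interval at N = 20 would describe post-transplant mortality better but would not make it comparable with waiting.

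**What to change.** - **Protocol 4.2.2:** remove the statement that the endpoints inform risk relative to the waiting list. Alternatively, keep the topic and state that a single-arm cohort of recipients cannot provide that comparison. What the endpoints do describe is one-year survival after transplant and the incidence of viremia in recipients of HCV-positive hearts.
- **Protocol 10.4.3 and SAP 1.4.3:** report 1-year post-transplant survival as x/n with a two-sided exact 95% confidence interval.
- **Number of patients:** reconcile 10 (Protocol Summary, 10.5) with 20 (5.4, 5.6), and use the reconciled N for that interval.

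Survival of recipients of HCV-negative hearts may be added as context on donor type, labelled as such, but it is not needed.

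The cost is a wording change and one interval from data already planned. The price is a more modest claim in 4.2.2.
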